Date	11/13/2019
Title	Clinical Utility of Postoperative Hemoglobin Testing Following Vaginal Hysterectomy and Reconstruction for Symptomatic Pelvic Organ Prolapse
Principle Investigator	[name]
Sub-Investigators	[name]
Research Specialist	[name], MS
Department	Urogynecology
Hatton #	19-111

Introduction:

- Obtaining a complete blood count (CBC) on post-operative day (POD) 1 to assess postoperative hemoglobin levels is routine practice at our institution after pelvic reconstructive surgery.
- There is minimal data supporting this practice. Multiple studies throughout the gynecology literature suggest that this is not a necessary or cost effective strategy to assess for postoperative anemia. ^{2,6,9,11}
- Most patients who require blood transfusion or reoperation for bleeding will show clinical signs of anemia. ^{2, 6, 7, 11} It is necessary to consider the entire clinical picture before initiating blood transfusion for postoperative anemia. ¹
- Although the individual cost of each lab test is low, the cumulative cost of these tests is substantial. ^{2,9}
- The procedure of choice for prolapse repair by Cincinnati Urogynecology Associates, TriHealth Inc. is a vaginal hysterectomy (TVH) with concurrent apical, anterior, and posterior compartment native tissue repairs as indicated. A review of the literature failed to identify any studies that have looked specifically at the utility of postoperative CBC after vaginal hysterectomy with prolapse repairs.

Purpose of Study

- To determine if checking a routine CBC results in clinically relevant changes to patient care in women undergoing pelvic reconstructive surgery with vaginal hysterectomy for treatment of pelvic organ prolapse.

Hypothesis or Research Question:

- We hypothesize that there is minimal utility in the routine collection of POD1 CBC in patients undergoing TVH during vaginal prolapse repairs.
- We also hypothesize that the overall blood transfusion rate of our pelvic reconstructive patients is low, and that a more selective approach to CBC collection would be appropriate.

Background:

Surgeons commonly check a CBC on patients after major gynecologic surgery. This is done to evaluate for postoperative anemia and to provide surgeon reassurance prior to discharging a patient home. There are more than 200,000 inpatient operative procedures completed for pelvic organ prolapse annually in the United States.⁵ Studies quote rates from, 87-99.6% of patients having a CBC drawn on POD1 and up to 1/3 of these patients requiring some intervention based on these results.^{6,7,11} Further evaluations of abnormal lab results may be additional blood work or more invasive procedures such as imaging tests or reoperation.

In recent years, multiple studies have shown that routine preoperative lab testing is not ubiquitously indicated for women undergoing gynecologic and urologic surgery. Thirty day outcomes do not change regardless of lab collection prior to surgery.³ The American Society of Anesthesia recommends against routine preoperative lab testing in the absence of clinical indications.¹⁴ Even with these recommendations, up to 40% of women receive un-indicated preoperative lab testing prior to urologic procedures.¹³ Similar to lab testing in the preoperative period, despite the high rate surgeons ordering postoperative labs, the clinical utility of a POD1 CBC has been called into question.

Throughout the gynecology literature, studies have identified multiple risk factors for a larger drop in hemoglobin on POD1 including hysterectomy at the time of pelvic surgery, midurethral sling placement at the time of prolapse repair, lower BMI, and the amount of IVF received in the OR.^{2,11} These findings were corroborated by additional studies, which also identified preoperative anemia, history of coagulopathy, and African American or Hispanic ethnicity as risk factors for postop blood transfusion.^{4,8,10,12} Although these patient and surgical characteristics have been identified as risk factors for postoperative anemia and transfusion, one study noted based on their data, that if they restricted CBC collection to patients with at 2 or more signs of anemia on POD1, 90% of their sample would not have required testing.⁷ Other studies have corroborated that almost all patients that ultimately require blood transfusion will show clinical signs of anemia.^{2,6,11}

Within our Division, the surgical procedure of choice to treat pelvic organ prolapse is a total vaginal hysterectomy with concurrent vaginal native tissue prolapse repairs. As standard practice, patients are kept overnight in the hospital for observation and a CBC is collected the morning on POD1. Studies in the gynecology literature have looked at the utility of routine CBC on patients after elective gynecologic surgery in general, total laparoscopic hysterectomy, minimally invasive sacrocolpopexy with or without concurrent hysterectomy, but none have looked specifically at our patient population having a vaginal hysterectomy with vaginal prolapse repairs.^{2,6,7,10}

Our goal is to show that routine collection of a CBC on POD1 in asymptomatic patients after vaginal hysterectomy with prolapse repair is unnecessary. If this is found, we could stop routine CBC collection which is a bothersome procedure for many patients and an added expense contributing to high health care costs.

Research Plan:

Study Design: Retrospective chart review

Setting of Study: TriHealth Epic platform at one of the various clinical locations.

Participants: All patients who underwent a total vaginal hysterectomy with concurrent vaginal native tissue prolapse repairs performed by one of four fellowship trained urogynecologists at TriHealth between 10/1/2014 and 10/1/2019. The patients will be identified by CPT codes in the EPIC electronic medical record.

Inclusion Criteria:

Total vaginal hysterectomy with or without bilateral salpingectomy/oophorectomy (CPT 58260, 58262, 58263, 58270, 58290, 58291, 58292, 58294)

At least one of the following vaginal native tissue prolapse repairs

Apical repair with uterosacral ligament suspension (CPT 57283)

Apical repair with sacrospinous ligament fixation (CPT 57282)

Anterior repair (CPT 57240, 57260, 57284, 57285, 57250)

Posterior repair (CPT 45560, 56800, 56810, 57200, 57210, 57250)

Age >18

Surgery by one of four fellowship trained urogynecologists at TriHealth

Exclusion Criteria:

Concomitant surgical procedure by a second surgeon

Malignancy identified at the time of surgery or active malignancy

Cases converted to open hysterectomy or prolapse repairs

Prolapse repair completed robotically

Prolapse repair completed with mesh

Known coagulopathy

Patient on long term preoperative anticoagulant medication (Arixtra, Coumadin, Eliquis, Heparin, Lovenox, Pradaxa, Savaysa, Xarelto)

Sample Size:

Similar retrospective studies included between 629-1105 patients in their chart review.^{2, 6, 7, 11} Based on the number of vaginal hysterectomies performed by our department annually, we anticipate five years of data collection will provide a comparable study size for this review. Our anticipated sample size will be approximately 800 patients.

Data Collection: Please see attached data collection sheet

- Charts of all patients having a total vaginal hysterectomy by one of our four fellowship trained urogynecologists during the study time frame will be identified and analyzed for inclusion and exclusion criteria.
- All charts meeting inclusion criteria will be included in the analysis.
- Each chart will be reviewed and the following variables collected for analysis:
 - Type(s) of prolapse repair(s)
 - Additional procedure for urinary incontinence at the same time as hysterectomy and prolapse repair – yes/no
 - Preoperative CBC collected within 30 days of surgery – yes/no
 - Preoperative hemoglobin
 - CBC collected the morning of POD1 – yes/no
 - POD1 hemoglobin
 - Change in hemoglobin from preoperative to postoperative collection
 - Change in hemoglobin level ≥ 2 – yes/no
 - Postoperative hemoglobin ≤ 10 – yes/no
 - More than one postoperative hemoglobin obtained – yes/no
 - Patient with objective signs of anemia (*persistent hemodynamic changes: pulse >100 beats per minute, blood pressure <90/60*) – yes/no
 - Patient with subjective signs of anemia (*dizziness, lightheadedness, weakness, pale, cool, diaphoretic*) – yes/no
 - Blood transfusion – yes/no
 - Estimated blood loss
 - IVF volume received intraoperatively
 - Length of surgery (in minutes)
 - Prophylactic heparin given preoperatively – yes/no
 - General demographic data including: name, DOB, age, race, BMI, medical comorbidities, parity, smoking history, menopausal status
 - Preoperative aspirin use – yes/no
 - Preoperative antiplatelet medication use (i.e.: Brilinta, Effient, Plavix) – yes/no
 - Stage of pelvic organ prolapse at preoperative appointment
 - Prior abdominal or pelvic surgery – yes/no
 - Patient readmitted within 30 days of surgery – yes/no

- Patient seen in emergency department within 30 days of surgery – yes/no
- Length of hospital stay (in days)
- Delay in discharge due to CBC results – yes/no

Intervention or experimental aspect of the study:

- No intervention will occur as part of this study.
- There are no potential risks to the study population by any aspect of this study.

Statistical Analysis:

Demographic data will be described using frequency (percentage) for categorical variables and mean (standard deviation) or median (min, max) for continuous variables. The percentage of subjects with hemoglobin less than 10 g/dL at POD1 will be evaluated as well as the percentage of subjects with signs of anemia. Pearson product moment correlation coefficient will be employed to measure the association between postoperative hemoglobin level and perioperative variables such as age, BMI, blood loss, or length of surgery. The mean hemoglobin change from pre- to postoperative measurement in symptomatic subjects will be compared with that of asymptomatic subjects using Student's t-test. Multiple linear regression will be used to investigate risk factors impacting mean decrease in hemoglobin. On the other hand, multiple logistic regression will be used to investigate factors associated with the presence of signs of anemia.

Ethical Considerations:**Informed Consent:**

- Informed consent will not be required given the retrospective chart review design of this study.

Privacy Information:

- Extensive effort will be made to ensure and maintain participant confidentiality. All identifying information will be maintained in a secure area at all times. All communication between staff members regarding participant data will occur via the Subject ID number only. However, identifying information will be retained in the original/source documents.
- The Excel spreadsheet will be stored on a password protected, encrypted TriHealth computer for ten years following study closure, and then purged.

Cost/Budget:

- This study will incur no cost to the institution, the participants, or the investigators.

Estimated Period of Time to Complete Study	
When will study begin?	Winter 2019
Protocol Development Completed	2 weeks
Admin Review Time	2 weeks
IRB Approval	3 weeks
Data Collection	4 weeks
Data Analysis	2 weeks
Presentation Development (if applicable)	2 weeks
Manuscript Development (if applicable)	4 weeks
Journal Submission Process (if applicable)	4 weeks
Study Closure	2 weeks

When and how will results be disseminated?

- The results will be disseminated by way of an oral or poster presentation at a national meeting and with publication in a high-impact journal.

References:

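### The plan aims to show that routine POD1 CBC is unnecessary and transfusion rare, but it does not analyse the outcomes bearing on either claim and has no rule that could reject them

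*Combined protocol and SAP*

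**What the plan says.** The Background sets a directional goal: "Our goal is to show that routine collection of a CBC on POD1 in asymptomatic patients after vaginal hysterectomy with prolapse repair is unnecessary". It then names the use of the result: "If this is found, we could stop routine CBC collection". Hypothesis or Research Question contains two claims. One is "We hypothesize that there is minimal utility in the routine collection of POD1 CBC in patients undergoing TVH during vaginal prolapse repairs". The other is that "the overall blood transfusion rate of our pelvic reconstructive patients is low". No section attaches a number to minimal, low or unnecessary.

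Statistical Analysis lists:
- two percentages: POD1 hemoglobin below 10 g/dL, and signs of anemia;
- Pearson correlations of postoperative hemoglobin with perioperative variables;
- a t-test of hemoglobin change, symptomatic against asymptomatic women;
- a linear regression for the fall in hemoglobin;
- a logistic regression for signs of anemia.

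Data Collection also includes transfusion, more than one postoperative hemoglobin, and discharge delay due to CBC results, each as yes/no. Statistical Analysis mentions none of the three.

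Sample Size rests on two things. One is resemblance to published work: "Similar retrospective studies included between 629-1105 patients in their chart review". The other is department volume, from which "we anticipate five years of data collection will provide a comparable study size for this review". The result: "Our anticipated sample size will be approximately 800 patients".

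**The concern.** Showing that a test is unnecessary, or that a rate is low, means showing that a proportion is below some ceiling. That needs an estimate of the right proportion, an upper confidence limit, and a ceiling fixed before the counts are known. The plan has none of these for either claim.

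The inferential methods answer other questions. A significant t-test would say that symptomatic women lost more hemoglobin, not that testing asymptomatic women changes nothing. A non-significant one would not show that the groups are alike. The regressions identify predictors of hemoglobin fall and of signs of anemia, and neither is a measure of utility.

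A practice decision is at stake. A small count of CBC-prompted events could be reported as no utility without a statement of what rate remains compatible with the data. A larger count could still be called low, because nothing was committed to in advance. The Background itself cites studies in which up to one third of tested patients needed some intervention on the result, so a negligible rate cannot be taken for granted.

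**Working it through.** **1. The plan's own figure.** The documents give no alpha, power, effect size, event rate, margin or target precision, so 800 cannot be derived. It lies within the cited 629 to 1105 and is a feasibility figure. The useful question is what about 800 charts could rule out.

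**2. Claims against planned analyses.**

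| Claim | Variable that bears on it (Data Collection) | In Statistical Analysis? |
|---|---|---|
| CBC unnecessary in asymptomatic women | discharge delay due to CBC; transfusion and repeat hemoglobin in women without signs | no |
| Transfusion rate low | transfusion | no |
| Neither directly | hemoglobin below 10 g/dL; signs of anemia | yes, as percentages without interval or limit |

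**3. What the proportions could show.** Every input here is an assumption. The 720 asymptomatic women are 90% of 800. The Background cites a 90% figure, but from another study using a rule of two or more signs, so it only suggests a scale. The 560 is 70% of 800, a less favourable case.

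The exact (Clopper-Pearson) one-sided 95% upper limit for x events in n is Beta⁻¹(0.95; x+1, n−x). For x = 0 it reduces to 1 − 0.05^(1/n).

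- n = 720, x = 0: 1 − 0.05^(1/720) = 0.42%
- n = 720, x = 1, 2, 3: 0.66%, 0.87%, 1.07%
- n = 560, x = 0: 1 − 0.05^(1/560) = 0.53%

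On one-sided limits with 720 women, a claim of below 1% survives at most 2 events, and a claim of below 0.5% survives only 0. With 560 women even 0 events does not support below 0.5%.

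**4. Sidedness matters.** The two-sided 95% interval uses 0.975 in place of 0.95. At 0 of 720 its upper limit is 1 − 0.025^(1/720) = 0.51%, so below 0.5% is then out of reach. The documents state no sidedness.

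**5. Transfusion overall.** For 8 of 800 (1%, assumed) the two-sided 95% interval is 0.43 to 1.96%. The same data pass a 2% limit and fail a 1% limit. With n = 800 and the two-sided upper limit, at most 2, 8 or 14 events keep it below 1%, 2% or 3%. If the true rate were 1%, the chance of 8 or fewer events is 59%, and of 14 or fewer, 98%.

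**6. Can the t-test stand in?** Assume 10% symptomatic (80 against 720), two-sided alpha 5% and a normal approximation. The standard error in SD units is √(1/80 + 1/720) = 0.118. The difference detectable with 80% power is (1.96 + 0.84) × 0.118 = 0.33 SD. Power for a true 0.2 SD difference is about 40%, so it would be missed about 60% of the time. Even a clear result would concern hemoglobin change, not change in care.

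**The case against.** This is a retrospective, largely descriptive review of all eligible charts over five years. A formal power calculation is not essential, and size is naturally set by feasibility. Purpose of Study is worded neutrally, as a question whether the CBC leads to relevant changes in care. Two of the planned outputs are plain rate estimates. Exact intervals without a pass/fail limit would also be a reasonable repair, and a CBC-prompted change in care is not necessarily a benefit to the patient.

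Much of this stands, and it rules out three stronger readings that a reader might infer:

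- *That every planned analysis looks for a difference.* The two percentages do not, although they do not measure utility and carry no interval.
- *That any result whatever could be read as support.* Very high rates would be hard to call low. If one third of 800 tested women needed intervention, that would be about 267. The documents support only the narrower statement that no pre-stated rule would reject either hypothesis.
- *That 800 charts are too few.* For rare events the precision is useful: 0 of 800 gives a two-sided upper limit of 0.46%.

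The illustration covers only small counts, and the documents give no rate for asymptomatic women. What the objection does not remove is the mismatch between a goal to show something, with stopping a routine test as the stated consequence, and an analysis that never estimates the relevant proportions.

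**Conclusion.** The concern holds in this form: followed as written, the plan cannot support its own conclusions. Its analysis section omits transfusion and CBC-attributed discharge delay, gives no interval, and sets no limit for either hypothesis. That rests on the text alone.

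The size of the consequence is illustrative, because the asymptomatic share, the event counts, the candidate limits and the sidedness are all assumed. Within those assumptions, moving the limit from 1% to 2% reverses the conclusion from 8 transfusions in 800. With 720 asymptomatic women, one event more or less (2 against 3, one-sided) decides a claim of below 1%.

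This is a gap in outcome and decision rule, not in the number of charts. It should be corrected before chart review, since a limit chosen after the counts are seen carries little weight.

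**What to change.** In Statistical Analysis, name two main outcomes:

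1. The proportion of asymptomatic women with a CBC-attributed change in care. Asymptomatic means neither objective nor subjective signs recorded. The numerator uses discharge delay due to CBC results, plus transfusion and repeat hemoglobin in those women. State how women without a POD1 CBC are handled.
2. The overall transfusion proportion.

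Report each with an exact (Clopper-Pearson) 95% interval, with one stated sidedness throughout. Before chart review, the investigators state and justify the largest value of each that they would call minimal or low. They conclude unnecessary or low only if the upper limit is below that value; otherwise they report not shown. Add to Sample Size a short table of the upper limits that about 800 charts can deliver. The correlations, t-test and regressions can stay as supporting analyses.

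The cost is more than wording. Only discharge delay is recorded as due to the CBC; transfusion and repeat hemoglobin carry no trigger. The composite outcome and the denominator must be written down, and one abstraction field for the trigger may be needed. No extra charts are required. The study also becomes able to fail to support its hypotheses.

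### The goal judges the whole day-1 CBC, but hemoglobin is the only CBC result listed or analysed, so a conclusion that the CBC is unnecessary would go beyond the data

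*Combined protocol and SAP*

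**What the plan says.** **Wording for the whole test.** Purpose of Study: "To determine if checking a routine CBC results in clinically relevant changes to patient care". The first hypothesis likewise concerns the utility of the routine day-1 CBC. The last paragraph of Background gives the goal, "Our goal is to show that routine collection of a CBC on POD1 in asymptomatic patients after vaginal hysterectomy with prolapse repair is unnecessary", and the consequence, "If this is found, we could stop routine CBC collection".

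**Wording for hemoglobin.** The title reads "Clinical Utility of Postoperative Hemoglobin Testing Following Vaginal Hysterectomy". The Introduction says: "Obtaining a complete blood count (CBC) on post-operative day (POD) 1 to assess postoperative hemoglobin levels is routine practice at our institution". Background adds: "This is done to evaluate for postoperative anemia and to provide surgeon reassurance prior to discharging a patient home". The second hypothesis concerns transfusion.

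**What is collected.** The Data Collection list has preoperative and day-1 hemoglobin, the change between them, two hemoglobin cut-offs, and "More than one postoperative hemoglobin obtained". It also has "Delay in discharge due to CBC results", a yes/no item with no reason attached. It names no white-cell or platelet value. The section refers to a separate abstraction form, which is not in the text available for this review.

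**What is analysed.** Statistical Analysis uses hemoglobin level, hemoglobin change and signs of anemia. It describes no summary of discharge delay or repeat testing.

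**The concern.** A CBC by definition also reports white-cell and platelet counts. If the routine draw is ended, all of those results are lost, so the quantity that bears on the decision is how often any of them changed care. The plan observes one component and words its conclusion for all of them.

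The gap lies in the group the goal is about. The only symptom or sign items in the list are signs of anemia, so asymptomatic can only mean free of those signs. A woman managed for a white-cell or platelet result could fall in that group with the action unrecorded. Since presentation and publication are planned, a conclusion worded for the CBC would be read by others as covering the whole test.

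**Working it through.** **The plan's own figure.** The only relevant number is the anticipated sample of about 800 women. It comes from feasibility and the size of similar studies (629 to 1105), with no precision target. It implies 800 / 5 = 160 eligible cases a year and lies inside the cited range. There is no formula to reproduce, and this point does not affect it.

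**How each kind of event would be recorded, from the Data Collection list:**

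| Event | Listed field | Component identifiable? |
|---|---|---|
| Discharge held because of hemoglobin | Delay item = yes | No reason field |
| Discharge held because of white-cell or platelet count | Delay item = yes | No reason field |
| CBC repeated because of white-cell or platelet count | Repeat-hemoglobin item = yes, since a repeat CBC returns a hemoglobin | No |
| Culture, imaging or treatment prompted by white-cell or platelet count | None | Not applicable |

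Length of stay and all-cause 30-day readmissions and emergency visits are also collected. They might reflect a later consequence, but carry no link to the CBC.

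**Direction.** Among n women, let H have a care change prompted by hemoglobin. Let F have one prompted by another component that shows up in the delay or repeat item, and let U have one prompted by another component that has no field. Assume no overlap, and that every H is recorded.

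- True CBC yield = (H + F + U) / n. Recorded yield = (H + F) / n. Shortfall = U / n, which is zero or more.
- If the recorded yield is read as hemoglobin's yield, the excess is (H + F)/n − H/n = F / n, which is also zero or more.

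So the CBC as a whole can look less useful than it was, and hemoglobin more useful than it was. The error has no single direction; it depends on which claim is made.

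**Size.** The documents give no rate for F or U. As an assumption, let 0.1% to 2% of women have an action prompted by another component (F and U together):

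- 800 × 0.001 = 0.8 women; 800 × 0.02 = 16 women.

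If the other components were collected and no such action were seen in 800, the exact upper 95% limit would be:

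- one-sided: 1 − 0.05^(1/800) = 0.37%
- two-sided: 1 − 0.025^(1/800) = 0.46%

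The assumed range lies on both sides of these limits, so it does not settle whether the omission is material. It shows that collecting the data would permit a bound, whereas actions with no field permit none. All 800 is the largest possible denominator; the asymptomatic group will be smaller, and its size is not given.

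**The case against.** The strongest reply is that CBC in this protocol is shorthand for the draw that yields a hemoglobin. The title, the Introduction's account of local practice, Background's reason for ordering and the transfusion hypothesis all point to anemia, and the variables fit that question. Much of this stands: it makes the gap one of scope and wording. It does not close the gap, because why a test is ordered does not tell us whether its other results change care once reported. The purpose asks about changes in care, and the consequence is to end the whole draw.

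Other points that stand:

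- The missing abstraction form may hold further fields, so the statement that hemoglobin is the only result rests on the protocol's list.
- Excluding known coagulopathy, active malignancy and long-term anticoagulation may make some non-hemoglobin actions rarer.
- No planned analysis links hemoglobin to delays or repeats, so mixing causes in those items distorts no prespecified estimate. It matters once they are reported as evidence of utility.

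Three stronger readings may tempt a reader, and the documents do not support them:

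- *That delays from other components will be counted as anemia-driven.* Nothing says so; they simply cannot be attributed.
- *That the omission can only favour the study's hypothesis.* Delays and repeats prompted by other components score yes, which raises the recorded yield.
- *That a specific number of women would be missed.* One could take 90% of 800 = 720 as sign-free and apply 0.5% to 2%, giving about 4 to 14. But the 90% is a cited study's share with fewer than two signs, which includes women with one; the action rate is assumed; and some of these actions do have a field.

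**Conclusion.** The point holds as a mismatch of scope. Followed as written, the plan can support a statement about day-1 hemoglobin testing for anemia, but not that the routine CBC is unnecessary. Actions prompted by white-cell or platelet results, other than a discharge delay or a repeat draw, have no listed field, and those two items cannot be assigned to a component.

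The size is unknown, and a material effect is not shown. The conclusion assumes that the Data Collection list is complete and that the goal means the CBC as worded. The sample size and planned tests are unaffected. It deserves correction because it changes what the study may conclude and costs little to put right.

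**What to change.** Choose one, preferably before abstraction starts.

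**(a) Narrow the claim.** Word the purpose, first hypothesis, goal and conclusion for routine day-1 hemoglobin testing for anemia. State that other CBC components were not evaluated. For each discharge delay attributed to the CBC, record whether hemoglobin was the charted reason. Cost: wording and one extra item for women with a delay. Downside: a narrower conclusion, which alone would not cover ending the whole CBC.

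**(b) Widen the data.** Add the day-1 white-cell and platelet counts. Where charted, record which component prompted each delay, repeat draw or other CBC-prompted action, with a category for trigger not charted. Add a line to Statistical Analysis reporting care changes for any component and for hemoglobin alone, with the number whose trigger is unknown. Cost: two numeric fields and a trigger code per chart, taken largely from a report already opened for hemoglobin. Downside: slightly longer abstraction, and some triggers will not be recoverable.

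Under either option, check the abstraction form first in case it already holds these fields.

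### With four surgeons over five years and no surgeon term in the plan, associations of surgeon-dependent variables with hemoglobin outcomes may be confounded and their standard errors understated

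*Combined protocol and SAP*

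**What the plan says.** Under Participants, the protocol restricts cases to those "performed by one of four fellowship trained urogynecologists at TriHealth between 10/1/2014 and 10/1/2019". The Inclusion Criteria repeat the restriction: "Surgery by one of four fellowship trained urogynecologists at TriHealth". A concomitant procedure by a second surgeon is an exclusion, so each patient should belong to one surgeon.

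The Data Collection section opens with "Data Collection: Please see attached data collection sheet" and then introduces an itemised list: "Each chart will be reviewed and the following variables collected for analysis". The list has repair type, incontinence procedure, estimated blood loss, intraoperative fluid and length of surgery. It has no operating surgeon and no date or year of surgery. The nearest entry is "General demographic data including: name, DOB, age, race, BMI, medical comorbidities, parity, smoking history, menopausal status". Date of birth with age would give the year of surgery only roughly, and only if age means age at surgery.

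The Statistical Analysis section plans Pearson correlations of postoperative hemoglobin with perioperative variables (age, BMI, blood loss and length of surgery are the examples), a t-test of hemoglobin change by symptom status, and two regressions. On the linear model it says only "Multiple linear regression will be used to investigate risk factors impacting mean decrease in hemoglobin". The logistic model for signs of anemia is described in the same way. Neither has a covariate list, and no surgeon term, calendar term or clustering method is named for any analysis.

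**The concern.** Several candidate predictors are things a surgeon can plausibly influence: how long the operation takes, how much blood is lost or recorded as lost, how much fluid is given, and which repairs and incontinence procedures are added. If surgeons also differ in their patients' hemoglobin drop, or in how signs of anemia are charted, a pooled analysis mixes differences between surgeons with differences among one surgeon's patients.

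Two things can then go wrong. If surgeon differences in the covariate and the outcome line up, the slope is biased. If they do not line up, the slope is right on average, but the usual standard error ignores the shared surgeon component and can be too small. In either case length of surgery, say, could be reported as a risk factor when it partly stands in for the surgeon. If the chart data contain no surgeon code, this cannot be examined afterwards.

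**Working it through.** **Inputs from the protocol.** Four surgeons and a window of five years (Participants). "Our anticipated sample size will be approximately 800 patients" (Sample Size). That number rests on feasibility and on earlier chart reviews ("Similar retrospective studies included between 629-1105 patients in their chart review"). It has no power calculation to reproduce; 800 lies inside the cited range.

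**Assumptions.** Caseload is spread evenly: 800 / 4 = 200 patients per surgeon. The documents give no intraclass correlation, so the share of variance due to surgeon is varied, for the outcome (ICCy) and for the covariate (ICCx).

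**Step 1: formula.** The variance of a pooled regression slope is inflated by about 1 + (m - 1) x ICCx x ICCy, with m = 200. For ICCy = 0.05 and ICCx = 0.05 this is 1 + 199 x 0.0025 = 1.498, and the standard error ratio is the square root, 1.22. If ICCx = 0 the factor is exactly 1, whatever ICCy is.

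**Step 2: false-positive rate.** Simulation with 4 x 200 patients, one covariate with no true effect within surgeon, independent surgeon effects on covariate and outcome, and 4000 replicates per row:

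| Outcome share | Covariate share | Variance factor | Rejection, no surgeon term | Rejection, surgeon fixed effects |
|---|---|---|---|---|
| 2% | 5% | 1.20 | 6.9% | 5.0% |
| 2% | 10% | 1.40 | 8.7% | 4.9% |
| 5% | 10% | 2.00 | 13.7% | 5.1% |
| 5% | 20% | 2.99 | 19.9% | 5.3% |
| 10% | 20% | 4.98 | 28.4% | 4.8% |

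A repeat with other random numbers gave about 29% for the last row, hence a range of about 7-29%. With a covariate share of 0-1% the pooled test stays at about 5-6% for outcome shares up to 5%. At 1% and 10% the factor is 1 + 199 x 0.001 = 1.20, as in the first row, so about 7% is to be expected there.

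**Step 3: bias and standard error.** Simulation with a true standardized slope of 0.20 and 2000 replicates, fitted without a surgeon term:

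- Outcome share 5%, covariate share 0: mean slope 0.199, empirical SD 0.0355, model SE 0.0351. No problem.
- 5% and 5%, surgeon effects independent: slope 0.199, SD 0.0408, SE 0.0354. The SE is 1 - 0.0354/0.0408 = 13% too small, with no average bias. The ratio 0.0408/0.0354 = 1.15 is below the 1.22 of Step 1, so the formula is only a rough guide with four surgeons.
- 5% and 5%, surgeon effects fully aligned: slope 0.236, a bias of 0.036/0.20 = 18%.
- 5% and 30%, fully aligned: slope 0.288, a bias of 0.088/0.20 = 44%. Full alignment is an extreme case.

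With surgeon fixed effects the mean slope was 0.199 to 0.201 and the model SE was close to the empirical SD in every setting (for example 0.0355 against 0.0355 at 5% and 5%, aligned).

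**The case against.** The strongest reply is that nothing in the documents shows that the four surgeons differ. They share a department and a preferred procedure, and no surgeon difference is reported. Confounding needs surgeon to be related to both covariate and outcome. A reader might infer that the risk-factor estimates are confounded and that all their standard errors are too small. The documents do not support that. Two of the four variables named for correlation are age and BMI, which need not vary much by surgeon, and for such variables the calculation shows almost no effect. This stands and limits the point to a possibility, for surgeon-dependent variables.

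A reader might also infer that surgeon is not collected at all, or is excluded from the models. Neither can be confirmed. The attached sheet is not available, and the regressions name no covariates whatever, so the accurate statement is that no surgeon adjustment is specified. Even if the sheet records surgeon, the analysis section does not say it will be used.

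The simulation has one covariate, which resembles the planned correlations more than the multiple regressions. A model with operative time, blood loss, fluid and repair type together might absorb part of a surgeon effect. The figures are therefore not error rates for the planned regressions, and no logistic model was simulated.

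For predicting hemoglobin drop within this one practice, the pooled association may also be of interest. That is a reason to show it beside the adjusted one, not to leave out the adjusted one.

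Finally, calendar year has no numerical support here. Practice may drift over five years, but that is only plausible, so year is a secondary matter.

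**Conclusion.** The gap is real and worth closing, with a limited reach. As printed, the plan cannot separate blood loss, length of surgery, intraoperative fluid, type of repair or incontinence procedure from the surgeon. Their associations with postoperative hemoglobin, hemoglobin drop or signs of anemia may be biased and may look more precise than they are.

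The size is unknown. The rejection range of about 7-29% rests on assumed variance shares, equal caseloads and a single covariate, and its upper end needs large surgeon differences (10% of outcome variance and 20% of covariate variance). With small surgeon differences in the covariate there is little or nothing to correct.

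It would be wrong to read this as undermining the study's main question. The stated purpose is whether a routine CBC changes care. The percentages with low hemoglobin or signs of anemia, and the counts of transfusions and delayed discharges, do not depend on these coefficients. Nor does the protocol say that a testing rule will be built from the regressions.

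**What to change.** Add operating surgeon (coded 1-4) and date of surgery to the variable list and, if they are not already there, to the data collection sheet. Both must be looked up to apply the eligibility criteria, so little extra abstraction is needed if this is done before charts are reviewed. Adding them later could mean reopening about 800 charts.

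In the Statistical Analysis section, state that surgeon enters the multiple linear regression as a fixed effect (three indicators), and that the associations of perioperative variables will be reported adjusted for surgeon. With only four surgeons, fixed effects are preferable to a random effect or cluster-robust standard errors. Add year of surgery as one linear term, as a secondary adjustment. Include the same terms in the logistic regression if the number of patients with signs of anemia supports them.

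The sample size does not change. The cost is three degrees of freedom for surgeon, or 3 + 1 = 4 with year, which is small beside about 800 patients in the linear model. In the logistic model the limit is the number of patients with signs of anemia, which the documents do not give. If events are few, the extra terms could overload that model, so the condition for including them should be written down in advance.
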